### 7.6.2 Primary Effectiveness Endpoint

- **Sensitivity to Analysis Set**

The hypothesis testing will be performed in the mITT analysis set for the acute effectiveness endpoint.

- **Best-case Scenario**

Subjects with missing acute effectiveness outcome data will be treated as a success in this analysis. The proportion of subjects who are acute effectiveness success will be estimated in the PP and mITT analysis sets.

- **Worst-case Scenario**

Subjects with missing acute effectiveness outcome data will be treated as a failure in this analysis. The proportion of subjects who are acute effectiveness success will be estimated in the PP and mITT analysis sets.

- **Tipping Point Analysis**

Tipping point analysis will be performed for the acute effectiveness endpoint to assess the impact of missing outcomes on the effectiveness conclusion. The proportion of subjects with acute effectiveness success will be updated one by one by incrementally treating a subject with a missing outcome as failure to evaluate whether a tipping point is identified. If the lower bound of the exact two-sided 95% confidence interval of an acute effectiveness success rate is less than the performance goal of 90%, then the tipping point is considered identified. Otherwise, no tipping point is found. The analysis will be performed in the PP and mITT analysis sets.

## 7.7 Subgroup Analyses

In order to provide additional characterization and interpretation of the primary endpoints, the following subgroup analyses will be performed. The mITT will be used for primary safety endpoint and PP analysis set will be used for primary effectiveness endpoint for the subgroup analyses. Descriptive statistics will be presented in each subgroup. No formal statistical hypothesis will be performed to test the differences between subgroups. Descriptive statistics will be presented with the number and proportion of subjects with events by subgroup of the following factors:

- Age group: <65 vs.  $\geq 65$  years
- Sex: Male vs. Female
- CHA2DS2-VASc Score:  $\leq 2$  vs.  $> 2$

## 7.8 Handling of Missing Data

### 7.8.1 Primary Safety Endpoint

If a subject has had a PAE or is adjudicated by CEC as having a PAE, regardless subject's follow-up duration, the subject will be considered having an event. If a

subject's follow-up time is less than 3 months and the subject has not had a PAE, that subject will be excluded from the primary safety endpoint analysis.

### **7.8.2 Primary Effectiveness Endpoint**

If a subject did not have adenosine/isoproterenol challenge performed or failed in checking entrance block for the targeted vein, the subject will be considered having a missing acute effectiveness endpoint.

### **7.8.3 Secondary Effectiveness Endpoint**

For the secondary effectiveness endpoint analysis, if a subject has an effectiveness failure at any time during the effectiveness evaluation period (Day 91-365), then the subject will be considered to have an event. Subjects who do not experience an effectiveness failure and do not have a full 12-month follow-up and/or sufficient follow-up duration for the secondary effectiveness endpoint (i.e., with at least 335 days of follow-up and arrhythmia monitoring post the index procedure) will be considered missing outcome for the secondary endpoint. These subjects will be censored on the date of their last follow-up for the Kaplan-Meier analysis.

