19.2 Sample Size Justification

Primary Safety Endpoint:

Based on a performance goal of 12% and assuming an anticipated primary safety event rate of 5% for the primary safety endpoint, a sample size of 135 subjects (with 5% missing data due to attrition) will provide above 80% power to reject the null hypothesis for the primary safety hypothesis test using a one-sided exact binomial test. The target significant level is 0.025.

Primary Effectiveness Endpoint:

Based on a performance goal of 90% and assuming an anticipated failure-free rate of 97% for the primary effectiveness endpoint, a sample size of 100 subjects will provide above 80% power to reject the null hypothesis for the primary effectiveness hypothesis test using a one-sided exact binomial test. The target significant level is 0.025.

Secondary Effectiveness Endpoint:

Based on a performance goal of 50% and assuming an anticipated failure-free rate of 65% for the secondary effectiveness endpoint, a sample size of 100 subjects (with 10% missing data due to attrition) will provide above 80% power to reject the null hypothesis test for the secondary effectiveness hypothesis using a one-sided exact binomial test. The target significant level is 0.025.

Total Sample size:

The sample size of this study is mainly driven by the hypothesis test for the primary safety endpoint. The total sample size for this study will be 135 subjects, based on the 135 subjects needed for the primary safety endpoint evaluation, 100 subjects for the primary acute effectiveness endpoint evaluation, and 100 subjects for the secondary effectiveness endpoint evaluation. A 5% attrition rate of the subjects for the primary safety endpoint and no attribution of the subjects for the primary effectiveness endpoints were assumed for the total sample size estimation.

A total of 135 evaluable subjects will be included in the study. Each of the four (4) subsets (NAE, CT/MRA, EE and PVI durability) will consist of 30 subjects and will be integrated within the study.

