19.4.6.1 Handling of Missing Data

- For the final primary safety analysis, if a subject does not have full 12 months of follow-up and the subject has had a PAE at any time during the follow-up, then the subject will be considered an event. If a subject does not have 12 months of follow-up but has at least 3 months of follow-up, then their last observed status will be carried forward for the 12-month safety endpoint as a conservative proxy. If a subject does not have at least 3 months of follow-up for the primary safety endpoint, then this subject will be excluded from the final primary safety analysis.

- For the final secondary effectiveness analysis, if a subject has an effectiveness failure at any time during the evaluation period, then the subject will be considered having an event. Subjects without an effectiveness failure who do not have full 12 months of follow-up will be excluded from the final effectiveness analysis.
- To investigate the robustness of the analysis result for the primary endpoints, several sensitivity analyses will be performed. Details on these analyses will be provided in SAP

20 Ethics and Protection of Human Subjects

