## 6. Sample Size Justification

- **Primary Safety Endpoint:**

Based on a performance goal of 12% and assuming an anticipated primary safety event rate of 5% for the primary safety endpoint, a sample size of 135 subjects (with 5% missing data due to attrition) will provide above 80% power to reject the null hypothesis for the primary safety hypothesis test using a one-sided exact binomial test. The target significance level is 0.025.

- **Primary Effectiveness Endpoint:**

Based on a performance goal of 90% and assuming an anticipated failure-free rate of 97% for the primary effectiveness endpoint, a sample size of 100 subjects will provide

more than 80% power to reject the null hypothesis for the primary effectiveness endpoint using a one-sided exact binomial test. The target significance level is 0.025.

- **Secondary Effectiveness Endpoint:**

Based on a performance goal of 50% and assuming an anticipated failure-free rate of 65% for the secondary effectiveness endpoint, a sample size of 100 subjects (with 10% missing data due to attrition) will provide above 80% power to reject the null hypothesis test for the secondary effectiveness hypothesis using a one-sided exact binomial test. The target significance level is 0.025.

- **Total Sample size:**

The sample size of this study is mainly driven by the hypothesis test for the primary safety endpoint. The total sample size for this study will be 135 subjects, based on the 135 subjects needed for the primary safety endpoint evaluation, 100 subjects for the primary acute effectiveness endpoint evaluation, and 100 subjects for the secondary effectiveness endpoint evaluation. The sample size estimation assumes a 5% attrition rate of the subjects for the primary safety endpoint and no and 10% attribution of the subjects for the primary and secondary effectiveness endpoints, respectively.

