## **7.10 Analyses of Secondary Effectiveness Endpoint**

If success is achieved in both the primary safety and acute effectiveness endpoints, then the secondary effectiveness endpoint will be evaluated using the exact test for a binomial proportion at a one-sided significance level of 2.5%. If the lower bound of the exact two-sided 95% confidence interval of the 12-Month effectiveness success rate is greater than the performance goal of 50%, the study will be considered to have demonstrated long-term (12-Month) effectiveness. Testing of the hypothesis for the secondary effectiveness endpoint ensures family-wise error rate is controlled at a 2.5% level after the success of the primary endpoints is met.

The secondary effectiveness endpoint will be performed in the PP analysis set when all subjects have completed their 12-month follow-up. The analyses results will be reported in the final CSR

The following additional analysis will be performed for the secondary effectiveness endpoint based on 12-month follow-up data:

- **Sensitivity to Analysis Set**

The secondary effectiveness endpoint will be analyzed in the mITT analysis set as a sensitivity analysis.

- **Kaplan-Meier Analysis**

Kaplan-Meier estimates and plots will be used to characterize the time to first failure event of the secondary effectiveness endpoint, including acute effectiveness failure, recurrence of documented symptomatic/asymptomatic AF/AT/AFL episodes during evaluation period. The probability of freedom from the secondary effectiveness endpoint failure at each follow-up timepoint post blanking will be presented. The KM analysis will be performed in the PP and mITT analysis sets.

- **Best-case Scenario**

The point estimate for freedom from secondary effectiveness failure will be estimated by treating subjects with missing secondary effectiveness outcomes as free from secondary effectiveness events.

- **Worst-case Scenario**

The point estimate for freedom from secondary effectiveness failure will be estimated by treating subjects with missing secondary effectiveness outcomes as failures.

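### The 12-month test counts early leavers only if they have already failed; this biases the success rate down by about 1 to 2 points and is missing from the stated power

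*SAP*

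**What the plan says.** **Test.** SAP 7.10 tests the 12-month success rate in the PP set with the "exact test for a binomial proportion at a one-sided significance level of 2.5"%, after both primary endpoints have succeeded. Success means a lower 95% bound above 50%.

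**Early leavers.** SAP 7.8.3 counts any failure in Day 91-365 as an event. It treats as having a missing outcome "Subjects who do not experience an effectiveness failure and do not have a full 12-month follow-up and/or sufficient follow-up duration", and puts the threshold for sufficient follow-up at 335 days of follow-up and monitoring. Protocol 19.4.6.1 is explicit about the consequence: "Subjects without an effectiveness failure who do not have full 12 months of follow-up will be excluded from the final effectiveness analysis". Acute procedural failures also count as 12-month failures (SAP 7.4.3).

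**Sample size.** SAP 6 sets the goal at 50%, takes 65% as the true rate, and claims for this endpoint: "a sample size of 100 subjects (with 10% missing data due to attrition) will provide above 80% power". Protocol 19.2 gives the same figures. On the trial as a whole, SAP 6 says: "The total sample size for this study will be 135 subjects".

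**Supporting analyses.** SAP 7.10 adds: "Kaplan-Meier estimates and plots will be used to characterize the time to first failure event of the secondary effectiveness endpoint". SAP 7.8.3 censors event-free leavers in that analysis. Best-case and worst-case estimates are also planned. None of these decides the test.

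**The concern.** The quantity of interest is the proportion of subjects free of failure through 12 months. The written rule estimates something else: event-free completers divided by completers plus those leavers whose failure was seen before they left. Failures among leavers enter the denominator; event-free leavers do not. This pulls the ratio down even if leaving is pure chance.

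The sample-size text takes no account of this. It appears to apply 65% to whatever remains after 10% attrition, which would be right only if all leavers were dropped alike. At stake are a slightly low reported 12-month rate, a confidence bound that belongs to a different quantity, and a power statement that does not match the analysis. A device that truly meets the goal is somewhat more likely to miss this claim.

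**Working it through.** **Inputs from the documents.** Goal 50%, assumed true rate 65%, one-sided exact test at 0.025, 100 subjects with 10% attrition, planned total 135 (SAP 6, SAP 7.10, protocol 19.2).

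**Input not in the documents.** *f*, the share of leavers' eventual failures that is seen before they leave. It is varied from 0 to 1.

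**Step 1: the plan's figure.** With exactly 90 analysed, the smallest number of successes with exact tail probability at most 0.025 under 50% is 55 (tail 0.0223). Power at 65% is 81.2%, so the stated figure is reproduced. If instead each of 100 subjects is lost at random with probability 0.10, so that the number analysed varies, average power is 79.6%. Dropping all leavers alike from 135 leaves 121 (rounded down), where the cut-off is 72 and power is 91.2%.

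**Step 2: the written rule.** Let *L* = 0.10 be the share leaving early, independent of outcome.

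- Kept successes: 0.65(1 − L) = 0.585.
- Dropped: L(1 − 0.35f).
- Expected tested rate: 0.585 / [1 − 0.10(1 − 0.35f)].

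For f = 0.5 this is 0.585 / 0.9175 = 63.8%; for f = 1 it is 0.585 / 0.935 = 62.6%.

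**Step 3: power under the rule**, averaged over the number analysed.

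| f | Expected rate | Power, 100 subjects | Power, 135 subjects |
|---|---|---|---|
| 0 | 65.0% | 79.6% | 90.5% |
| 0.25 | 64.4% | 76.5% | 88.2% |
| 0.5 | 63.8% | 73.1% | 85.5% |
| 0.75 | 63.2% | 69.5% | 82.3% |
| 0.9 | 62.8% | 67.2% | 80.2% |
| 1 | 62.6% | 65.7% | 78.8% |

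At 135, power stays above 80% unless f exceeds about 0.91. With 15% leavers and f = 0.5 it is 79.2%. Simulation with 3% acute failures (from the assumed 97% acute success) and several timings of dropout and recurrence gave expected rates of 62.7% to 64.0%, a bias of about 1 to 2 points.

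**Step 4: type I error.** At a true 50% and f = 0.5, the expected tested rate is 0.45 / [1 − 0.10(1 − 0.5 × 0.5)] = 0.45 / 0.925 = 48.6%. The false-success rate is about 1%, below 2.5%.

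**Step 5: would Kaplan-Meier do better?** In simulation with a log-log 95% bound and completers counted at risk to the end, the estimate averages 65.0%, with power 81-84% at 100 and 91-93% at 135, and one-sided type I error 2.0-2.2%. But 12-month visits fall on Day 335-379, with a Holter at the visit (protocol 13.5). Suppose completers are censored at their last visit, 20-30% of post-blanking failures are first found at that Holter (an assumption), and visits spread over the window. Then Day-365 power at 135 is about 77-81%, against about 86% for the existing rule. If all visits precede Day 365, with an assumed 10% share, it falls to about 35%. Carrying completers to the end of the window restores 65% and about 91%.

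**The case against.** **The trial plans 135 subjects, not 100.** This stands. A reader might infer that the 12-month test is underpowered, at 67-75%. The documents do not support that: those values apply at 100 subjects and need f of roughly 0.36 to 0.91. At 135 the target is not shown to be missed. The PP set and the long-term exclusions in SAP 7.1.3 could bring the number nearer to 100, but no rate for them is given, so that fall cannot be asserted. What remains is that the documents attach their power statement to 100, and there it does not follow from the rule they state.

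**The bias is conservative.** This also stands. The rule makes no false claim of effectiveness more likely, and study success rests on the two primary endpoints alone. The cost is a lower chance of a true secondary claim and a reported rate that is a little low.

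**The plan already has Kaplan-Meier and best-case and worst-case analyses.** In part. They will show the reader a less biased figure, but they cannot change the decision or correct the power text.

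**Kaplan-Meier is the obvious replacement.** A reader might infer that a simple swap is safe. Neither document says how an event-free completer last seen before Day 365 is handled, and without that rule the swap can do worse than the present test.

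**Conclusion.** The point holds in a limited form. Both documents make inclusion of early leavers depend on outcome, and the power calculation ignores it. The tested rate is low by 0 to 2.4 points, which is at most 16% of the 15-point margin between 65% and 50% (2.4 / 15). Power is about 66-80% at 100 subjects and about 79-90% at 135. The statement of above 80% at 100 holds only for exactly 90 analysed at an unbiased 65%.

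These ranges assume a true 65%, 10% leaving early, and dropout independent of outcome; the position within each range depends on *f*, which the documents do not supply. Nothing here inflates type I error or threatens the primary conclusions. It should be corrected, but it does not undermine the trial.

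**What to change.** **Minimum.** In SAP 6 and protocol 19.2 (and the same text in the protocol summary), restate the secondary-endpoint power under the actual missing-data rule, at 100 and at 135, with the assumption on *f* shown. For example: about 73% and 85% if half of leavers' failures are seen before they leave. This costs wording only.

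**Alternative.** In SAP 7.8.3 and 7.10 and protocol 19.4.5 and 19.4.6.1, let the planned Kaplan-Meier estimate in the PP set decide: success if the log-log 95% lower bound exceeds 50%, acute failures as events at Day 0, event-free leavers before Day 335 censored at last follow-up, and the exact binomial test kept as a sensitivity analysis. The text must also state that event-free subjects with at least 335 days of follow-up and monitoring count as event-free through Day 379, and that the estimate is read there. Because the endpoint runs to Day 365, it should say how a recurrence first recorded on Day 366-379 is counted.

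The costs are an asymptotic rather than exact interval, an assumption of non-informative censoring (which the best-case and worst-case analyses probe), and a protocol amendment. Protocol 10.2 requires approval before a substantial modification is implemented. Either choice should be fixed before the 12-month data are analysed.

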19.3 Analysis Sets

Safety Population Analysis Set (SP): The SP analysis set will consist of all enrolled subjects who have had insertion of the study catheter, regardless of energy delivery.

Modified Intention-To-Treat (mITT) Analysis Set: The mITT analysis set will consist of enrolled subjects who meet eligibility criteria and have had insertion of the study catheter.

Per Protocol (PP) Analysis Set: The PP analysis set will consist of subjects who satisfy the following criteria:

- Have undergone ablation using PF and/or RF energy via the investigational ablation system per CIP
- Are treated for the study-related arrhythmia
- Are enrolled and without major CIP deviation that would affect the scientific integrity of the safety and effectiveness, including but not limited to the following:
 - Subjects found not meeting eligibility criteria
 - Failure to check for entrance block for each targeted PV after adenosine/isoproterenol challenge.

- Use of the investigational ablation system outside the PV region. A CTI line for documented typical AFL identified prior to or during the procedure using investigational system or commercial RF devices to complete the procedure is allowed during index or repeat ablation procedure (within blanking). For the treatment of arrhythmia outside the PV region, using commercial RF devices to complete the procedure is allowed. However, subjects using commercial RF devices for the non-PV regions and/or CTI lines will be excluded from the 12-month effectiveness analysis.
- Missing all CIP specified electrocardiographic effectiveness monitoring

Neurological Assessment (NA) Analysis Set: The NA analysis set will include 30 subjects who have had pre-and post-index-ablation procedure MRI and neurological assessments completed. Subjects with no pre-index ablation procedure MRI assessment and no lesions observed on post-MRI assessment will be included for analysis.

Esophageal Endoscopy (EE) Analysis Set: The EE analysis set will include 30 subjects who have had a readable 1 to 3 days post index-ablation procedure esophageal endoscopy assessment.

Cardiac CT/MRA Analysis Set: The CT/MRA analysis set will include 30 subjects who have readable outcomes at baseline and 3 months.

PVI Durability Analysis Set: The PVI durability analysis set will include 30 subjects who have readable electro-anatomical mapping at index ablation procedure and 75 days (+/-15 days) post index ablation procedure.

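### The 335-day monitoring condition for a 12-month success sets no minimum amount of rhythm data, and Kaplan-Meier censors at last follow-up instead of last recording; both lean towards passing the 50% goal

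*SAP*

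**What the plan says.** **Rule for an observed outcome.** Under SAP 7.8.3, a subject without a failure who lacks full 12-month follow-up and/or sufficient duration, explained as "with at least 335 days of follow-up and arrhythmia monitoring post the index procedure", "will be considered missing outcome for the secondary endpoint". Protocol 19.4.6.1 asks only for a full 12 months of follow-up and says nothing about rhythm data.

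**Per-protocol set.** Both documents exclude subjects with no monitoring at all (Protocol 19.3: "Missing all CIP specified electrocardiographic effectiveness monitoring"; SAP 5 is equivalent). The list of exclusions is open-ended in both.

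**Monitoring schedule.** Protocol 13.5.2 asks for at least one transmission of 30 seconds or more each week from the 1-month visit through month 5, then monthly to month 12, plus transmissions whenever symptoms occur. It adds 24-hour Holters at 3, 6 and 12 months and a 12-lead ECG at visits.

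**Analyses.** SAP 7.10 has the endpoint "evaluated using the exact test for a binomial proportion at a one-sided significance level of 2.5" per cent, in the per-protocol set. Supporting analyses are the mITT set, Kaplan-Meier, and best- and worst-case treatment of missing outcomes. On Kaplan-Meier, SAP 7.8.3 says of subjects with a missing outcome: "These subjects will be censored on the date of their last follow-up for the Kaplan-Meier analysis".

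**The concern.** The endpoint includes asymptomatic episodes and is seen only on recordings. A subject who keeps attending but seldom records has little chance of being found a failure. Three features of the plan allow this to pass untested:

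- The monitoring half of the 335-day condition has no content beyond its duration. There is no minimum number or share of transmissions, no required Holter and no required recording late in follow-up.
- Kaplan-Meier uses the last contact, not the last time rhythm was observed, as the end of event-free time.
- The missing-data scenarios start from subjects already classed as missing. A sparsely monitored subject classed as a success is never questioned.

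There is no control arm in which under-detection could offset itself. It moves the observed rate straight towards the fixed goal.

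**Working it through.** **1. The plan's own figure.** SAP 6 sets the goal at 50% and the assumed success rate at 65%. Its power statement is that "a sample size of 100 subjects (with 10% missing data due to attrition) will provide above 80% power". With n = 100 less 10% = 90, the smallest r with P(X ≥ r | n, 0.50) ≤ 0.025 is r = 55 (exact level 0.0223). Power is P(X ≥ 55 | 90, 0.65) = 81.2%. At n = 100, r = 61 and power is 82.8%. The stated power is reproduced.

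**2. What the schedule delivers from Day 91 to Day 365.**
- Weekly strips, Day 91-180: (180 − 91)/7 = 12.7, about 13. Monthly strips, months 6 to 12: 7. Total about 20 × 30 s = 10 minutes at the stated minimum.
- Holters: 3 × 24 = 72 h, or 48 h if the 3-month Holter falls before Day 91 (the visit window is Day 76-104).
- Strips as a share of scheduled strip and Holter time: 10/(72 × 60 + 10) = 0.23% to 10/(48 × 60 + 10) = 0.35%.

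A subject who misses every Holter therefore loses over 99% of this scheduled time. Visit ECGs and symptom-triggered strips are not in the count.

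**3. How the condition can be met.** Intermittent monitoring cannot supply 335 days of continuous observation, so the condition has to be a span or a standard of adherence. No standard is written down. Read as a span, a few strips with one at or after Day 335 would satisfy it, and such a subject has not missed all monitoring either.

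**4. Illustration of the consequence.** The documents give no adherence rate, so the undetected share d of failures is assumed. If a share u of failing subjects is poorly monitored and a share s of their failures is still found, then d = u(1 − s). For example, u = 10%, s = 0.5 gives d = 5%; u = 20%, s = 0.5 gives d = 10%.

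Observed success = true success + d × (1 − true success). At a true 50%, d = 5% reads as 52.5% and d = 10% as 55.0%. The chance of passing is P(X ≥ r | n, observed success):

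| n | r | d = 0 | d = 5% | d = 10% |
|---|---|---|---|---|
| 90 (100 less 10%) | 55 | 2.2% | 6.2% | 14.5% |
| 121 (135 less 10%) | 72 | 2.3% | 7.3% | 18.3% |
| 135 (no loss) | 80 | 1.9% | 6.8% | 18.2% |

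**5. Margin at the planned effect.** At n = 121 and an observed 65%, successes number 0.65 × 121 ≈ 79 against a cut-off of 72. Eight successes recounted as failures (79 − 8 = 71) would lose the claim.

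**The case against.** A reader might infer that only subjects with no monitoring at all are kept out of the analysis, or that unmonitored time in general is counted as arrhythmia-free. The documents do not support either. The no-monitoring exclusion defines the per-protocol set; SAP 7.8.3 is a second filter that makes failure-free subjects missing when follow-up or monitoring is too short. Time after last follow-up is censored in Kaplan-Meier, and those subjects leave the exact test. Nor do the documents establish that a subject with one late strip is scored a success. The condition could also be read as monitoring kept up to Day 335.

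Other points also stand. Kaplan-Meier is a supporting analysis, so its censoring rule cannot change the tested conclusion. The mITT, best-case and worst-case analyses are real safeguards for outcomes classed as missing. Visit ECGs and symptom-triggered strips add detection, a missed test counts as a deviation (Protocol 16), and the sponsor undertakes to track missing data (Protocol 23.1.3). The undetected shares of 5% and 10% have no source in the documents.

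None of this supplies a minimum of rhythm data, tests sparsely monitored subjects classed as successes, or justifies contact over observation as the censoring date.

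**Conclusion.** The point holds in this form: the SAP has a monitoring condition, but it can be met as a span with few recordings; the protocol's counterpart has no such condition; Kaplan-Meier censors subjects with a missing outcome at last contact; and no planned analysis challenges sparsely monitored successes. The direction of bias is towards success, because an absent recording can hide a failure and cannot create one. The size is unknown. The rise from about 2% to 6.2-7.3% (d = 5%) or 14.5-18.3% (d = 10%) shows sensitivity to an assumption and is not an estimate. It should be corrected before the 12-month data are analysed, because the 'and/or' in SAP 7.8.3 and the undefined term leave the choice of reading open until then.

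**What to change.** In SAP 7.8.3 and 7.10:

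1. Censor Kaplan-Meier at the last core-lab-readable rhythm recording. State the rule for failure-free evaluable subjects too, since the current sentence covers only those with a missing outcome.
2. Add one sensitivity analysis of the binomial endpoint. Failure-free subjects with no readable Holter in Day 91-365, or below a pre-stated share of scheduled transmissions, count as missing and, in its worst case, as failures. Report monitoring compliance alongside it. The sponsor must choose and justify the share, as the documents give no basis for one. Requiring just one readable recording in the 12-month window would not be enough, because a single late strip would meet it.
3. Reconcile the full 12 months in Protocol 19.4.6.1 with the 335-day follow-up-and-monitoring condition, and resolve the 'and/or'.

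**Cost.** SAP wording, one sensitivity table and a compliance summary; no change to visits or procedures. Some subjects move from success to missing in the sensitivity analysis, and Kaplan-Meier follow-up is slightly shorter. Because detected failures stay in while poorly monitored successes drop out, the analysis leans conservative and should be read as a bound. Numbers allow it: "The total sample size for this study will be 135 subjects", and power at the assumed 65% is 91.2% with 121 evaluable and still 81.2% with 90.
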